Official Title: Immunologic response to influenza vaccination

ClinicalTrials.gov ID (NCT number): NCT03614975

Protocol Date: September 20, 2018

Scientific Background:

The Advisory Committee on Immunization Practice (ACIP) sets civilian immunization policy for the United States. In adults, cell-based recombinant vaccine has been shown to work better immunologically against the H3 strain due to lack of egg-based adaptations; however, it is not licensed for use in children. All of the published efficacy trial data on Flucelvax, the cell-based influenza vaccine approved by the FDA in 2012, were conducted when it was based on the egg-adapted strain; it first used the cell-based strain in the Fall of 2017 so effectiveness data have not been published on this update. Egg-based vaccine has only worked reasonably well against the H3 in preliminary effectiveness data for younger children; it did not work well against H3 in adult recipients due to egg-based adaptations. This study would be among the first head-to-head comparison of the current versions of these two different licensed influenza vaccines to compare the differences in antibody response among children/teens/young adults. Given recent changes in the formulation of Flucelvax and the lack of published data on this new formulation, reasonable equipoise can be assumed among these vaccines.

Influenza is a major public health burden, each year causing millions of illnesses and outpatient visits and tens of thousands of hospitalizations and deaths in the U.S. The primary influenza prevention method is vaccination; however, influenza vaccine effectiveness (VE) is variable. Host factors (e.g., age and antibody landscape), environment (e.g., tobacco exposure), virus and vaccine characteristics, such as the match between the vaccine and circulating strains, contribute to VE. This project will quantify pre- and post influenza immune response to different influenza vaccine types licensed for use (e.g., egg-based, egg-free).

Study Objectives:

Using a RCT for children 4-20 years of age, two influenza vaccines will be assessed for their immunogenic outcomes: Flucelvax (egg-free inactivated flu shot) and Fluzone (egg-based inactivated flu shot).

The study objectives are to determine the serologic, proteomic and/or peripheral blood mononuclear cells (PBMCs)/RNA responses to:

1) cell-based quadrivalent influenza vaccine (Flucelvax) and 2) egg-based quadrivalent influenza vaccine (Fluzone) in a randomized controlled trial (RCT) among racially diverse children 4-20 years of age.

Study Design and Methods:

We will conduct a non-blinded, randomized controlled trial of influenza vaccine immunogenicity in children aged 4-20 years. Influenza vaccination will occur in primary care settings with standard medical care use according to CDC guidelines with FDA approved and licensed vaccines. Bloodwork will be conducted at baseline and post-vaccination for research purposes during the vaccination season (e.g., August thru December).

Parents of child/teen patients will be asked to complete the appropriate screening questionnaire which addresses inclusion and exclusion criteria in lay language where possible. If they do not meet all inclusion criteria, have an exclusion criterion, or are unwilling to complete study activities then they will not be eligible for enrollment and will not be consented by the clinician. The screening questionnaire may be done in person, by phone, by mailed form or by electronically sent form. The questionnaire takes <10 minutes to complete.

Research coordinators will meet with parents and children/teens to review study requirements and provide the written informed consent form for them to read through. Licensed doctoral level medical providers (e.g., MDs) or licensed pharmacists (e.g., PharmD) will be present either in person or by electronic device (e.g., face time) to address any parent's/child/teen's questions regarding the study and to obtain written consent (parents) and assent (children/teens), including written permission from parents to access their child's electronic medical record (EMR) in order to obtain data related to medical history, medication use, and vaccination history.

Randomization to licensed flu vaccine arms: Non-blinded randomization will be generated by computers and done as a 1:1 allocation to each of the licensed flu vaccine arms. Influenza vaccine will be given by clinical staff as part of the child/teen's routine immunization care. Influenza vaccine information will be collected via EMR review and/or documented at baseline using a research form noting the type of influenza vaccine received (e.g., vaccine manufacturer, valence, brand name).

Blood draws will be done at UPMC or Children's clinical recruitment practices. All participants will have a blood draw at baseline (may be during summer before vaccination) and at two subsequent follow-up visits. Total blood volume drawn across the study visits is ~90 mL (~30 mL drawn at each study visit). If not enough blood is obtained during study visit we will ask participants to return for an additional blood draw(s) in order to obtain the volume needed for analysis in the same study visit window; total volume for re-draws dependent upon tube type needed to fill (e.g, CPT tube for PBMCs, paxgene tube for RNA, serum tube for HI). Addendum consents for blood re-draws will be signed prior to drawing blood.

All blood samples will be collected by trained personnel with experience drawing blood from children. The blood samples will be collected using Vacutainer tubes, with uniformly colored tops according to type of processing and appropriately labeled with a uniform scheme (including study ID and collection time point). To support better understanding of the immune response following influenza vaccination, specimens will be banked for future studies that might involve proteomics, immunology, transcriptomics, or genomics. Collection of survey data done at UPMC clinical recruitment practices. Survey data will be collected from all enrolled participants at the baseline visit. If participant time constraints limits collection of the survey at the baseline visit, this information will be collected at a subsequent study visit.

Cells will be prepared and frozen according to current protocols. Plasma and cells will be stored at -80C until all specimens are collected. They will be inventoried and maintained in a database in the laboratory. Upon completion of sample collection (pre-vacc, and postvacc) samples will be sent to the funder and other contracted laboratories for further analysis. Peptoid and other laboratory testing will be conducted per current protocols.

Specific to East Liberty Family Health Center (ELFHC) clinical recruitment site: ELFHC clinical staff's (e.g., MA/RN) activities will be limited to 1) helping to identify potential subjects, drawing blood on and providing influenza vaccination to consented and enrolled participants. Pitt research staff along with the specified MD will conduct the informed consent process with parents and children/teens and/or adult (18-20 years) participants and Pitt research staff will administer the survey at this site. Prior to staffing ELFHC for study recruitment, ELFHC helping with this research project will complete the Community Partner Research Education and Training (CPRET) prior to engagement in research activities. This training will be conducted by the Principal Investigator.

All participants will have a blood draw at baseline and at two subsequent follow-up visits. Total blood volume drawn across the study visits is ~90 mL (~30 mL drawn at each study visit: baseline, 2nd study visit, 3rd study visit). If another blood draw visit needs to be scheduled due to lack of volume collected at the prior visit (e.g., unable to collect total per visit mLs due to participant dehydration) or due to poor recovery of PBMCs, then additional blood will be collected dependent upon the type of tube needed. In some circumstances (e.g., inadequate vacuum draw/clotting issue/observed hemolysis), up to an extra tube (e.g., up through 10mL) may be drawn at any particular visit. Research staff Phlebotomists are fully trained in phlebotomy with appropriate clinical phlebotomy experience (e.g., experience with drawing blood on children). Clinical site/hospital lab Phlebotomists are fully trained and employed by UPMC. ELFHC clinical staff are fully trained in phlebotomy and vaccination.

Specific endpoints that will result in withdrawal from the study include non-compliance with allotted windows for visits in study protocol. Baseline blood draw and 2 return blood-draw visits: day 7 (range 6-9 days) and day 21 (range 21-35 days). Acceptability of samples with minor deviations from these windows will be determined by the research team on a case-by-case basis. Persons who do not meet these criteria will be dropped from the study. Onset of a new severe bleeding disorder that precludes further phlebotomy. If a participant misses day 7 but can still make the day 21 visit, they may be retained.

The PI and co-investigators will monitor the progress of the research study, including assessments of data quality and timeliness and participant recruitment, accrual and retention, subject's confidentiality, any adverse event data, unanticipated problems and external factors or relevant information that might have an impact on the safety or ethics of the study. The PI and co-investigators will meet on a regular basis to discuss these

issues. Minutes will be recorded for each of the meetings which will occur on a bimonthly to quarterly basis, depending on the stage of the study. At the time of the IRB renewal the PI will submit in writing to the IRB a summary report of the data and safety monitoring activities from the past year. The CDC and University of Pittsburgh will hold phone calls at least quarterly to address the progress of the research study, including assessments of data quality and timeliness and participant recruitment, accrual and retention, subject's confidentiality, any adverse event data, unanticipated problems and external factors or relevant information that might have an impact on the safety or ethics of the study. Minutes will be recorded for each of the meetings. Adverse events will be reported to the HRPO per its Policies and Procedures Manual.

Eligibility Criteria:

Inclusion Criteria:

1. Males and females aged 4-20 years whose prior vaccination history is available (which can be determined based on the medical record or state registry for the prior year or participation in our previous studies of childhood influenza vaccine (previous participants are a high priority for enrollment);
2. Planning to receive seasonal influenza vaccination at one of our recruiting sites
3. \geq 37 pounds

Exclusion Criteria:

1. Unable or unwilling to complete all required study activities, including informed consent and bloodwork
2. Already received the influenza vaccine for the current year
3. Have a known immunocompromising condition or on an immunosuppressing medication (e.g., high dose steroids)
4. Known to be pregnant
5. Have a history of severe allergy to eggs or to influenza vaccine or any of its components

Statistical Considerations:

As an initial step in the data analysis, descriptive statistics will be generated for each of the variables of interest, including their distributional properties. Through analyses of these distributional property assessments and relevant statistical tests, the necessary assumptions for the planned statistical tests will be investigated. If the assumptions are not met for any planned statistical test, then either the data will be transformed or a nonparametric alternative will be used.

For the analysis of the survey data, methods appropriate for the analysis of counts and proportions, depending on the specific question will be used. Due to the distributional shape in geometric mean titers (GMT), either nonparametric tests or transformation of the data will be needed; log transformation will be used for the primary endpoint. The analysis will be conducted with transformed data. The natural log of the

GMT will be the dependent variable to normalize the distribution. The mean and standard deviation of log titers will be calculated. Exact tests will be used where needed for small cell sizes. Regression models will also be used for predictors of immunogenic outcomes.

Power calculations show the need to enroll 40 per vaccine arm with 74 per vaccine arm preferred for publication; we have noted 90 enrolled per arm to account for possible attrition. A one-sided, two-sample t-test with group sample sizes of 40 and 40 achieves 98% power to detect a ratio of 2.0 when the ratio under the null hypothesis is 1.0. The coefficient of variation on the original scale is 1.0. The significance level (alpha) is 0.050. A one-sided, two-sample t-test with group sample sizes of 74 and 74 achieves 80% power to detect a ratio of 2.0 when the ratio under the null hypothesis is 1.0. The coefficient of variation on the original scale is 4.0. The significance level (alpha) is 0.050.

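### The between-arm comparison makes no stated use of prior-season vaccination, although history is an entry condition; prespecified adjustment would be a nearly free gain in precision

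*Combined protocol and SAP*

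**What the plan says.** The only text on allocation, in Study Design and Methods, is that "Non-blinded randomization will be generated by computers and done as a 1:1 allocation to each of the licensed flu vaccine arms". It names no stratification factor, block or minimisation.

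Under Eligibility Criteria, inclusion criterion 1 makes an available vaccination history a condition of entry. The history can come from the medical record or state registry for the prior year, or from "participation in our previous studies of childhood influenza vaccine (previous participants are a high priority for enrollment". Study Design and Methods also has parents give permission for vaccination history to be taken from the electronic record, and every participant has blood drawn at baseline.

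Scientific Background lists "Host factors (e.g., age and antibody landscape" among the things that contribute to vaccine effectiveness. It does not name earlier vaccination.

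Statistical Considerations makes the log titre the dependent variable and sizes the trial on an unadjusted comparison: "A one-sided, two-sample t-test with group sample sizes of 40 and 40 achieves 98% power to detect a ratio of 2.0" and, for the larger size, "A one-sided, two-sample t-test with group sample sizes of 74 and 74 achieves 80% power to detect a ratio of 2.0". One further sentence foresees regression to look for predictors of the immune outcomes. It names no covariate for the comparison of the arms, no interaction and no subgroup.

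**The concern.** A variable that may well be related to titre is established at entry, and recruitment is tilted towards a group partly defined by it. The plan then states no use of it in the comparison that the trial is sized for. Two things are at stake.

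- **Chance imbalance.** With 40 to 90 children per arm, the arms can differ noticeably in the share vaccinated last season. In that particular trial, an unadjusted GMT ratio carries the difference.
- **A single averaged ratio.** If the cell/egg difference depends on recent vaccination, one pooled ratio averages over a mix set by how many earlier participants return. The plan neither fixes that share nor commits to reporting the ratio by history. The background rationale turns on egg adaptation and says that Flucelvax first used the cell-based strain in Fall 2017. That makes the question worth describing, but no passage says that the contrast varies with history.

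**Working it through.** **Inputs from Statistical Considerations.** Ratio 2.0 (ln 2 = 0.693), one-sided test, "The significance level (alpha) is 0.050"; 40 per arm with "The coefficient of variation on the original scale is 1.0"; 74 per arm with "The coefficient of variation on the original scale is 4.0"; 90 enrolled per arm.

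**Assumptions, not in the documents.** Share vaccinated last season p = 0.5 (range to 0.8); fold difference in titre by prior-season vaccination f = 1.5 to 3.

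**1. The plan's own power.** SD on the log scale = sqrt(ln(1 + CV²)), which is 0.833 for CV 1.0 and 1.683 for CV 4.0. The one-sided noncentral t gives 97.96% at 40 per arm and 80.2% at 74. Both stated figures reproduce.

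**2. Chance imbalance under unstratified 1:1 allocation.** SD of the between-arm difference in share = sqrt(2p(1-p)/n), and the 95% range is ±1.96 SD. With p = 0.5:
- n = 40: 1.96 × sqrt(0.5/40) = 0.219
- n = 74: 1.96 × sqrt(0.5/74) = 0.161
- n = 90: 1.96 × sqrt(0.5/90) = 0.146

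A difference above 10 percentage points has probability 37%, 22% and 18% respectively. With p = 0.8 these fall to 26%, 13% and 9%.

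**3. Shift in the GMT ratio.** Factor = exp(±difference × ln f), with p = 0.5:

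| n per arm | f = 1.5 | f = 2 | f = 3 |
|---|---|---|---|
| 40 | 0.91-1.09 | 0.86-1.16 | 0.79-1.27 |
| 74 | 0.94-1.07 | 0.89-1.12 | 0.84-1.19 |
| 90 | 0.94-1.06 | 0.90-1.11 | 0.85-1.17 |

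**4. Against ordinary sampling error.** The 95% margin on the ratio is exp(1.96 × SD × sqrt(2/n)):
- 40 per arm, CV 1.0: exp(1.96 × 0.833 × 0.2236) = 1.44
- 74 per arm, CV 4.0: exp(1.96 × 1.683 × 0.1644) = 1.72

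Variation due to vaccination history is part of the between-person CV, so the shifts in step 3 lie inside these margins and do not add to them.

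**5. Validity.** In a simulation of the unadjusted t-test (50,000 trials per case, p = 0.7, total SD at CV 1.0, 40 and 74 per arm, f = 1, 2, 3), the mean shift was about zero and the one-sided type I error was 0.048 to 0.052.

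**6. What adjustment buys on average.** Share of log variance due to history: R² = p(1-p)(ln f)²/SD². With residual variance (1 - R²)SD² and one further degree of freedom lost, for p = 0.5 to 0.7 and f = 1.5 to 3:
- 40 per arm, CV 1.0: power rises from 98.0% to between 98.4% and just over 99.9%.
- 74 per arm, CV 4.0: power rises from 80.2% to between 80.6% and 84.0%.

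**7. What adjustment buys after an unlucky allocation.** Take p = 0.5, with the imbalance at its upper 95% limit and favouring one arm. By normal approximation, the conditional one-sided error of the unadjusted test is P(Z > (1.645 × SE - shift)/SE_res). Here SE uses the total SD and SE_res the residual SD. At 40 per arm, CV 1.0, f = 2: SE = 0.186, shift = 0.219 × 0.693 = 0.152, SE_res = 0.169, so (0.306 - 0.152)/0.169 = 0.91 and the error is about 0.18. For f = 1.5 and 3 it is about 0.11 and 0.32. At 74 per arm, CV 4.0, the range is 0.08 to 0.14. An imbalance the other way lowers the error.

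**The case against.** The strongest reply is that nothing here is wrong with the plan as a randomised comparison. Every unstratified baseline variable can be unbalanced by chance, and the t-test's standard error already allows for it. The conditional errors in step 7 describe an extreme allocation, and averaged over allocations the error is 0.05. The share and fold effect are assumptions, and a 3-fold effect would make history about 44% of the log variance at CV 1.0. The average gain in power is small. All of this stands, and it limits the point to precision and single-trial imbalance.

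It is also fair that the documents are silent, which is different from ruling stratification or adjustment out. The regression sentence leaves room for covariates. It does not commit to any for the arm comparison, so the gap in prespecification remains.

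A reader might infer three stronger things that the documents do not support:
- **That carry-over from earlier vaccines biases the contrast.** Under random allocation it does not.
- **That the pooled ratio describes no one.** An average over the eligible population is the usual target of a randomised trial, and the objective is stated for children aged 4-20 as a whole.
- **That baseline titre cannot stand in for vaccination history because children with equal titres respond differently.** No passage says so.

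**Conclusion.** The point holds as a low-cost improvement in the analysis. Vaccination history is required at entry, and no use of it is stated in the allocation or in the arm comparison. The unadjusted contrast remains unbiased with valid alpha, and no stated sample size or power figure is wrong.

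The size is modest against the planned ratio of 2.0. With half the sample vaccinated last season and a 1.5- to 3-fold effect, the largest shift in step 3 (a factor of 1.27) is about 35% of ln 2, and the smallest (1.06, at the 90 enrolled) about 9%. The shares and fold effects are assumptions throughout. Any gain from adjusting for baseline titre is additional and cannot be sized from the documents.

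**What to change.** In Statistical Considerations, prespecify the between-arm comparison as a regression of log post-vaccination titre on arm, prior-season vaccination (yes/no, from the record already collected) and log baseline titre. Report the GMT ratio separately for children vaccinated and not vaccinated in the prior season, with the arm-by-history interaction labelled descriptive. Because inclusion criterion 1 also accepts earlier study participation as a source of history, say how prior-season status is coded where the record does not settle it.

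Stratifying the allocation by prior-season vaccination is optional and adds little beyond adjustment. If it is used, the trial being open-label calls for concealed, varying block sizes or minimisation, and the Randomization paragraph should say so.

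The cost is a few lines of analysis text. The subgroup ratios will have wide intervals and should be presented as such.

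### Is the sample size unsupported because 40 and 74 per arm rest on different coefficients of variation and no attrition rate is given?

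*Combined protocol and SAP*

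**What the plan says.** The whole sample-size argument is in the last paragraph of Statistical Considerations. It opens with "Power calculations show the need to enroll 40 per vaccine arm with 74 per vaccine arm preferred for publication" and continues in the same sentence with "we have noted 90 enrolled per arm to account for possible attrition".

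Two calculations follow. Both use a one-sided two-sample t-test, a null ratio of 1.0, an alternative ratio of 2.0 and alpha 0.05.

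- First: "A one-sided, two-sample t-test with group sample sizes of 40 and 40 achieves 98% power to detect a ratio of 2.0", with "The coefficient of variation on the original scale is 1.0".
- Second: 74 per arm for 80% power, with "The coefficient of variation on the original scale is 4.0".

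Study Design and Methods sets visit windows for day 7 and day 21 and says "Persons who do not meet these criteria will be dropped from the study". It also lets the team accept small departures from the windows case by case, allows a participant who misses day 7 to stay in for day 21, and provides for repeat draws when the volume is short. No expected rate of loss is given anywhere.

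**The concern.** The two sample sizes look like a minimum and a preferred version of one calculation, but they differ in both CV and power. A reader could take 40 as adequate and 74 as a bonus for publication. If the CV behind the 74 is the true one, 40 evaluable per arm give only 57% power.

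The reason offered for 74 is a publication preference, not a variance estimate. The 40 is worded as a number to enrol, whereas a t-test calculation returns a number analysed. With no attrition rate, the step to 90 cannot be traced to a stated input.

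Two things would be at stake. If variance is high and loss heavy, the trial could be underpowered. If variance is low, it could enrol more children than this calculation needs, each giving blood at three visits ("Total blood volume drawn across the study visits is ~90 mL").

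**Working it through.** **Inputs, all from Statistical Considerations:** ratio 2.0 against 1.0; one-sided alpha 0.05; log-transformed titers; CV 1.0 with 40 per arm; CV 4.0 with 74 per arm; 90 enrolled per arm. Loss rates of 10%, 20% and 30% are assumptions made here.

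**Formulas.** For log-normal data the SD on the natural-log scale is √ln(1 + CV²). The difference to detect is ln 2 = 0.693. The non-centrality parameter is 0.693 / (SD × √(2/n)), with 2n − 2 degrees of freedom. Power is the non-central t probability beyond the one-sided 5% critical value.

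**Step 1: the plan's own figures.**

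- CV 1.0: SD = √ln 2 = 0.833. With n = 40 the non-centrality is 3.72 and the critical value 1.665. Power is 98.0%; the plan states 98%.
- CV 4.0: SD = √ln 17 = 1.683. With n = 74 the non-centrality is 2.50 and the critical value 1.655. Power is 80.2%; the plan states 80%.

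Both reproduce.

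**Step 2: what the two CVs span.** The variance ratio is ln 17 / ln 2 = 2.833 / 0.693 = 4.1. The plan therefore covers about a four-fold range in log-scale variance.

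**Step 3: the implied attrition allowance.** From 90 to 74 it is 1 − 74/90 = 17.8%. From 90 to 40 it is 1 − 40/90 = 55.6%. Only the first is a plausible allowance, so 74 at CV 4.0 is the natural base for 90.

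**Step 4: power with 90 enrolled per arm.**

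| Assumed loss | Evaluable per arm | CV 1.0 | CV 2.0 | CV 3.0 | CV 4.0 |
|---|---|---|---|---|---|
| 0% | 90 | >99.9% | 98% | 92% | 87% |
| 10% | 81 | >99.9% | 97% | 89% | 83% |
| 17.8% | 74 | >99.9% | 95% | 87% | 80% |
| 20% | 72 | >99.9% | 95% | 86% | 79% |
| 30% | 63 | 99.9% | 92% | 82% | 74% |

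The largest CV that keeps 80% power is 5.6 with 90 evaluable, 4.65 with 81, 4.03 with 74 and 3.87 with 72.

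**Step 5: the figure of 40.** With 40 evaluable, power is 98%, 78%, 65% and 57% at CV 1.0, 2.0, 3.0 and 4.0, and 80% holds only up to a CV of about 1.9. Falling to 40 from 90 means losing 50 participants per arm.

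**The case for a change.** The case for acting is that the reader has to infer what the plan should state. The section never says that 74 is the base, that CV 4.0 governs, or that about 18% loss is expected. The required number depends strongly on the CV: for 80% power it is 19 per arm at CV 1.0 and 74 at CV 4.0. The unstated loss rate also decides whether 80% is held at CV 4.0, since 74 evaluable just reach it and 72 just miss. The remedy would cost a few sentences. The eligibility criteria mention "participation in our previous studies of childhood influenza vaccine (previous participants are a high priority for enrollment", so the team may hold data on titer variability and retention.

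The facts in this stand: neither the source of the CVs nor the loss rate is in the document. The consequences drawn from them are weaker.

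- The 40 is the lower of two scenarios, and nothing in the plan stops recruitment there. The sentence that speaks of enrolling 40 also gives 90 as the number enrolled, so its wording does not mislead about the size of the trial.
- The visit-window rule is softened by the case-by-case tolerance, the day 7 exception and the repeat draws.
- The excess-enrolment argument needs a CV near 1.0, which the documents cannot establish. It also treats this calculation as the only reason for 90, although the objectives include proteomic and cell/RNA responses, specimens are to be banked, and regression on predictors is planned.
- The earlier studies are cited only for vaccination history and recruitment priority. Whether titers were measured in them is unknown.

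**Conclusion.** No change to the plan is needed. The powers are correct for their stated inputs, and quoting a low and a high CV is an ordinary way to show uncertainty about variance. Enrolment is set above the more demanding scenario, so the trial does not depend on the favourable CV. Power falls clearly below 80% only if the CV is at or near 4.0 and loss is well beyond 17.8%. Even at 30% loss and CV 4.0 it is 74%.

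What remains is a gap in the written rationale, which a reader can fill by taking 74 at CV 4.0 as the base. Filling it would leave the 90 per arm, the test and the conclusions as they are.

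This rests on three assumptions: log-normal titers, as the plan's use of a CV with a log-scale analysis implies; a true CV not much above the plan's upper value; and the loss rates used above, which are illustrative.

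### Power rests on a one-sided 0.05 test with no favoured vaccine named, although the question is non-directional; two-sided, the 74-per-arm, CV 4.0 scenario has 70% power, not 80%

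*Combined protocol and SAP*

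**What the plan says.** The power paragraph under Statistical Considerations gives two scenarios. Both use a one-sided two-sample t-test at alpha 0.050, with a ratio of 1.0 under the null and 2.0 under the alternative.

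- Minimum size: "A one-sided, two-sample t-test with group sample sizes of 40 and 40 achieves 98% power", at a CV of 1.0 on the original scale.
- Larger size: "A one-sided, two-sample t-test with group sample sizes of 74 and 74 achieves 80% power to detect a ratio of 2.0". For this scenario, "The coefficient of variation on the original scale is 4.0".

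The two sizes are introduced together: "Power calculations show the need to enroll 40 per vaccine arm with 74 per vaccine arm preferred for publication". The plan then enrols 90 per arm to allow for attrition.

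The analysis text in the same section specifies natural-log titers ("GMT will be the dependent variable to normalize the distribution"), a nonparametric fallback and regression for predictors. It does not say whether the vaccine comparison will be one-sided or two-sided.

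On direction, the Scientific Background describes a head-to-head study "to compare the differences in antibody response among children/teens/young adults" and concludes that "reasonable equipoise can be assumed among these vaccines". The Study Objectives are to determine the responses to each vaccine and put neither one ahead. The one pointer to a direction is in the background: "In adults, cell-based recombinant vaccine has been shown to work better immunologically against the H3 strain". The background adds that egg-based vaccine performed poorly against H3 in adults.

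**The concern.** A one-sided test answers one question: is a named vaccine better than the other? The plan never names that vaccine. Its stated purpose is to compare two licensed quadrivalent products under equipoise, so a clear difference in either direction would be a finding.

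The consequences depend on what the final test turns out to be, and the plan leaves this open. The two cases are alternatives and do not add up.

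- **Final test two-sided at 0.05.** The quoted power belongs to a different test. At CV 4.0 the real power is lower than the reader is told.
- **Final test one-sided at 0.05.** A twofold advantage in the untested direction could not be declared. Because no direction is fixed in advance, it could be chosen once the data are known, which amounts to a two-sided test at 0.10.

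**Working it through.** **Inputs, all from the power paragraph:** ratio 2.0 against a null of 1.0; alpha 0.05; 40 per arm with CV 1.0; 74 per arm with CV 4.0; 90 enrolled per arm.

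**Method.** Two-sample t-test on log titers:

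- log-scale SD = √ln(1 + CV²)
- difference δ = ln 2 = 0.6931
- standard error SE = SD × √(2/n)
- power from the non-central t distribution with 2n − 2 degrees of freedom and non-centrality δ/SE

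**Log-scale SDs**

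- CV 1.0: √ln 2 = 0.8326
- CV 4.0: √ln 17 = 1.6832

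**Step 1: reproduce the plan's figures (one-sided 0.05)**

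- 40 per arm, CV 1.0: SE = 0.8326 × √(2/40) = 0.1862; non-centrality 3.723; critical value 1.665; power **98.0%** (stated 98%).
- 74 per arm, CV 4.0: SE = 1.6832 × √(2/74) = 0.2767; non-centrality 2.505; critical value 1.655; power **80.2%** (stated 80%).

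Both agree, so the method matches the plan's. At CV 4.0, 74 is also the smallest size that reaches 80% one-sided (73 gives 79.7%).

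**Step 2: change only the sidedness (two-sided 0.05)**

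| Per arm | CV | Non-centrality | Critical value | One-sided power | Two-sided power |
|---|---|---|---|---|---|
| 40 | 1.0 | 3.723 | 1.991 | 98.0% | 95.7% |
| 74 | 4.0 | 2.505 | 1.976 | 80.2% | 70.1% |
| 90 (no attrition) | 4.0 | 2.762 | 1.973 | 86.6% | 78.5% |

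**Step 3: what 80% two-sided power would take at CV 4.0**

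- 94 evaluable per arm for a ratio of 2.0 (93 gives 79.8%). That is more than the 90 to be enrolled.
- Alternatively, a true ratio of 2.18 with 74 per arm, or 2.03 with 90 per arm.

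**Step 4: dependence on the CV.** With 74 per arm, two-sided power is 99.9% at CV 1, 91.0% at CV 2, 78.8% at CV 3 and 70.1% at CV 4. It falls below 80% at a CV of about 2.9 with 74 per arm and about 3.8 with 90 per arm.

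**Step 5: the untested direction.** If the test is one-sided and the true ratio is 0.5 rather than 2.0 (74 per arm, CV 4.0), the chance of rejecting is below 0.01%.

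**The case against.** The strongest reply has four parts.

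1. **Nothing is miscalculated or hidden.** The test, alpha, CV and ratios are all given, and any statistician can convert the figures. This is true. What is missing is the direction and the sidedness of the final test, and a reader cannot recover either.

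2. **A direction can be inferred.** The adult H3 evidence favours a non-egg vaccine, Flucelvax is listed first, and the alternative ratio is above 1. The equipoise sentence may be there to justify randomising rather than to state a hypothesis. This is a fair reading for H3, but the evidence concerns adults and one strain, and the better response is credited to a recombinant vaccine that the background says is not licensed for children. The same section says egg-based vaccine did reasonably well against H3 in younger children, in preliminary data, and that published data on the new Flucelvax formulation are lacking. The plan does not turn any of this into a hypothesis for these products, these ages or the other strains.

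3. **The loss is confined to one scenario.** The stated need is 40 per arm at CV 1.0, where two-sided power is still 95.7%. The plan does not say that CV 4.0 applies to the primary endpoint. This stands and limits the severity.

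4. **Baseline adjustment could recover the power.** Every participant has a baseline sample. If the comparison were adjusted for baseline log titer, so that the SD shrinks by √(1 − ρ²), two-sided power at 74 per arm and CV 4.0 would be about 74% at an assumed correlation of 0.3 and 82% at 0.5. The plan does not commit to this adjustment and gives no correlation, so the 70% figure holds for the unadjusted test the plan names.

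**Conclusion.** The concern holds and should be fixed. The arithmetic is right for a one-sided test, but that test is unsupported by the stated question, and the final test is unspecified.

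At CV 4.0, the 74-per-arm size reaches 80% power only because one side was chosen. Two-sided, the chance of missing a true twofold difference rises from about 20% to about 30%. Since 74 of 90 implies attrition of 1 − 74/90 = 18%, retention between that level and 100% gives two-sided power between 70.1% and 78.5%, which is below 80% throughout. The 40-per-arm, CV 1.0 scenario is not materially affected.

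These figures assume log-normal titers with the same CV in both arms, an unadjusted t-test and a true ratio of 2.0. How far they apply to this trial depends on the CV of the primary endpoint, which the documents leave open between 1.0 and 4.0.

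**What to change.** Under Statistical Considerations, state that the vaccine comparison will be tested two-sided at alpha 0.05 and reported with a 95% confidence interval for the geometric mean titer ratio. Restate the power for a ratio of 2.0 as 96% (40 per arm, CV 1.0), 70% (74 per arm, CV 4.0) and 78% (90 per arm with no attrition, CV 4.0).

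If a one-sided test is really intended, the present figures can stand. The plan must then name the favoured vaccine and the strain or strains, justify the direction for this age range, and say that the final analysis is one-sided.

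Either route takes a few sentences and changes neither enrolment nor conduct. The cost of the two-sided route is that the plan openly states power just under 80% at CV 4.0, even with all 90 per arm evaluable.
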